**8.2.3.2.2. Unsolicited AEs**

The investigator will assess the maximum intensity that occurred over the duration of the event for all unsolicited AEs (including SAEs) recorded during the study. The assessment will be based on the investigator's clinical judgement.

The intensity should be assigned to one of the following categories:

1 (mild)	= An AE which is easily tolerated by the subject, causing minimal discomfort and not interfering with everyday activities.
2 (moderate)	= An AE which is sufficiently discomforting to interfere with normal everyday activities.
3 (severe)	= An AE which prevents normal, everyday activities  (in a young child, such an AE would, for example, prevent attendance at school/kindergarten/a day-care centre and would cause the parent(s)/LAR(s) to seek medical advice.)

An AE that is assessed as Grade 3 (severe) should not be confused with a SAE. Grade 3 is a category used for rating the intensity of an event; and both AEs and SAEs can be assessed as Grade 3. An event is defined as 'serious' when it meets one of the pre-defined outcomes as described in Section 8.1.2.

**8.2.3.3. Assessment of causality**

The investigator is obligated to assess the relationship between the investigational vaccine and the occurrence of each AE. The investigator will use clinical judgement to determine the relationship. Alternative plausible causes, such as natural history of the underlying diseases, concomitant therapy, other risk factors, and the temporal relationship of the event to the investigational vaccine will be considered and investigated. The investigator will also consult the IB and/or SmPC and/or Prescribing Information for marketed products to determine his/her assessment.

There may be situations when a SAE has occurred and the investigator has minimal information to include in the initial report to GSK Biologicals. However, it is very important that the investigator always makes an assessment of causality for every event prior to submission of the Expedited Adverse Events Report to GSK Biologicals. The investigator may change his/her opinion of causality in light of follow-up information and update the SAE information accordingly. The causality assessment is one of the criteria used when determining regulatory reporting requirements.

In case of concomitant administration of multiple vaccines/products, it may not be possible to determine the causal relationship of general AEs to the individual vaccine/product administered. The investigator should, therefore, assess whether the AE could be causally related to vaccination rather than to the individual vaccines/products.

All solicited local (injection site) reactions will be considered causally related to vaccination. Causality of all other AEs should be assessed by the investigator using the following question:

*Is there a reasonable possibility that the AE may have been caused by the investigational vaccine/product?*

**YES** : There is a reasonable possibility that the vaccine(s)/product(s) contributed to the AE.

**NO** : There is no reasonable possibility that the AE is causally related to the administration of the study vaccine(s)/product(s). There are other, more likely causes and administration of the study vaccine(s)/product(s) is not suspected to have contributed to the AE.

The definitions for 'NO' and 'YES' have been written in such a way that all events that have been attributed a 'NO' can be pooled with events which in the primary vaccination study were determined to be 'not related' or 'unlikely to be related' to vaccination. Those events that are attributed a 'YES' can be pooled with those events that in the past were determined to have a 'suspected' or 'probable' relationship to vaccination in the primary vaccination study.

If an event meets the criteria to be determined as 'serious' (see Section 8.1.2), additional examinations/tests will be performed by the investigator in order to determine ALL possible contributing factors for each SAE.

Possible contributing factors include:

- Medical history.
- Other medication.
- Protocol required procedure.
- Other procedure not required by the protocol.
- Lack of efficacy of the vaccine(s)/product(s), if applicable.
- Erroneous administration.
- Other cause (specify).

#### **8.2.3.4. Assessment of outcomes**

The investigator will assess the outcome of all unsolicited AEs (including SAEs) recorded during the study as:

- Recovered/resolved.
- Recovering/resolving.
- Not recovered/not resolved.
- Recovered with sequelae/resolved with sequelae.

- Fatal (SAEs only).

#### 8.2.3.5. Medically attended visits

For each solicited and unsolicited symptom the subject experiences, the subject's parent(s)/LAR(s) will be asked if the subject received medical attention defined as hospitalisation, or an otherwise unscheduled visit to or from medical personnel for any reason, including emergency room visits. This information will be recorded in the eCRF.

### 8.3. Prompt reporting of serious adverse events and other events to GSK Biologicals

SAEs that occur in the time period defined in Section 8.2 will be reported promptly to GSK within the timeframes described in [Table 19](#), once the investigator determines that the event meets the protocol definition of a SAE.

pIMDs that occur in the time period defined in Section 8.2 will be reported promptly to GSK within the timeframes described in [Table 19](#), once the investigator determines that the event meets the protocol definition of a pIMD.

**Table 19 Timeframes for submitting serious adverse events and pIMDs reports to GSK Biologicals**

Type of Event	Initial Reports		Follow-up of Relevant Information on a Previous Report	
	Timeframe	Documents	Timeframe	Documents
SAEs	24 hours*‡	electronic Expedited Adverse Events Report	24 hours*	electronic Expedited Adverse Events Report
pIMDs	24 hours**‡	electronic Expedited Adverse Events Report	24 hours*	electronic Expedited Adverse Events Report

\* Timeframe allowed after receipt or awareness of the information.

\*\*Timeframe allowed once the investigator determines that the event meets the protocol definition of a pIMD.

‡ The investigator will be required to confirm review of the SAE/pIMD causality by ticking the 'reviewed' box in the electronic Expedited Adverse Events Report within 72 hours of submission of the SAE/pIMD.

**8.3.2. Completion and transmission of SAE reports to GSK Biologicals**

Once an investigator becomes aware that a SAE has occurred in a study subject, the investigator (or designate) must complete the information in the electronic Expedited Adverse Events Report **WITHIN 24 HOURS**. The report will always be completed as thoroughly as possible with all available details of the event. Even if the investigator does not have all information regarding a SAE, the report should still be completed within 24 hours. Once additional relevant information is received, the report should be updated **WITHIN 24 HOURS**.

The investigator will always provide an assessment of causality at the time of the initial report. The investigator will be required to confirm the review of the SAE causality by ticking the 'reviewed' box in the electronic Expedited Adverse Events Report within 72 hours of submission of the SAE.

**8.3.2.1. Back-up system in case the electronic reporting system does not work**

If the electronic reporting system does not work, the investigator (or designate) must complete, then date and sign a paper Expedited Adverse Events Report and fax it to the Study Contact for Reporting SAEs (refer to the [Sponsor Information](#)) or to GSK Biologicals Clinical Safety and Pharmacovigilance department within 24 hours.

This back-up system should only be used if the electronic reporting system is not working and NOT if the system is slow. As soon as the electronic reporting system is working again, the investigator (or designate) must complete the electronic Expedited Adverse Events Report within 24 hours. The final valid information for regulatory reporting will be the information reported through the electronic SAE reporting system.

**8.3.3. Reporting of pIMDs to GSK Biologicals**

Once a pIMD is diagnosed in a study subject (whether serious or non-serious), the investigator (or designate) must complete the information in the electronic Expedited Adverse Events Report **WITHIN 24 HOURS** after he/she becomes aware of the diagnosis. The report allows to specify that the event is a pIMD and whether it is serious or non-serious. The report will always be completed as thoroughly as possible with all available details of the event, in accordance with the pIMD standard questionnaire provided. Even if the investigator does not have all information regarding a pIMD, the report should still be completed within 24 hours. Once additional relevant information is received, the report should be updated **WITHIN 24 HOURS**.

The investigator will always provide an assessment of causality at the time of the initial report. The investigator will be required to confirm the review of the pIMD causality by ticking the 'reviewed' box in the electronic Expedited Adverse Events Report within 72 hours of submission of the pIMD.

Refer to Section [8.3.2.1](#) for back-up system in case the electronic reporting system does not work.

**8.3.4. Updating of SAE and pIMD information after removal of write access to the subject's eCRF**

When additional SAE or pIMD information is received after removal of the write access to the subject's eCRF, new or updated information should be recorded on the appropriate paper report, with all changes signed and dated by the investigator. The updated report should be faxed to the Study Contact for Reporting SAEs (refer to the [Sponsor Information](#)) or to GSK Biologicals Clinical Safety and Pharmacovigilance department within the designated reporting time frames specified in [Table 19](#).

**8.3.5. Regulatory reporting requirements for serious adverse events**

The investigator will promptly report all SAEs to GSK in accordance with the procedures detailed in Section [8.3](#). GSK Biologicals has a legal responsibility to promptly notify, as appropriate, both the local regulatory authority and other regulatory agencies about the safety of a product under clinical investigation. Prompt notification of SAEs by the investigator to the Study Contact for Reporting SAEs is essential so that legal obligations and ethical responsibilities towards the safety of other subjects are met.

Investigator safety reports are prepared according to the current GSK policy and are forwarded to investigators as necessary. An investigator safety report is prepared for a SAE(s) that is both attributable to the investigational vaccine and unexpected. The purpose of the report is to fulfil specific regulatory and GCP requirements, regarding the product under investigation.

**8.4. Follow-up of adverse events/SAEs****8.4.1. Follow-up during the study**

After the initial AE report, the investigator is required to proactively follow each subject and provide additional relevant information on the subject's condition to GSK Biologicals (within 24 hours for pIMDs and SAEs; refer to [Table 19](#)).

All MAEs, pIMDs (serious or non-serious) SAEs and AEs leading to withdrawal from the study documented at a previous visit/contact and designated as not recovered/not resolved or recovering/resolving will be reviewed at subsequent visits/contacts until the subject is discharged from the study.

All other AEs documented at a previous visit/contact and designated as not recovered/not resolved or recovering/resolving will be reviewed at subsequent visits/contacts until 30 days after the last vaccination through Day 415 (or until the subject is discharged from the study, whichever is earliest).

**8.4.2. Follow-up after the subject is discharged from the study**

The investigator will follow subjects with SAEs, pIMDs (serious or non-serious), or subjects withdrawn from the study as a result of an AE, until the event has resolved,

subsided, stabilised, disappeared, or until the event is otherwise explained, or the subject is lost to follow-up.

If the investigator receives additional relevant information on a previously reported SAE or pIMD, he/she will provide this information to GSK Biologicals using a paper/electronic Expedited Adverse Events Report as applicable.

Follow-up of other non-serious AEs is required during the study only, as specified in Section 8.4.1.

GSK Biologicals may request that the investigator performs or arranges the conduct of additional clinical examinations/tests and/or evaluations to elucidate as fully as possible the nature and/or causality of the AE. The investigator is obliged to assist. If a subject dies during participation in the study or during a recognised follow-up period, GSK Biologicals will be provided with any available post-mortem findings, including histopathology.

## **8.5. Treatment of adverse events**

Treatment of any AE is at the sole discretion of the investigator and according to current good medical practice. Any medication administered for the treatment of an AE should be recorded in the subject's eCRF (refer to Section 6.7).

## **8.6. Subject card**

Subjects' parent(s)/LAR(s) must be provided with the address and telephone number of the main contact for information about the clinical study.

The investigator (or designate) must therefore provide a "subject card" to each subject's parent(s)/LAR(s). In an emergency situation this card serves to inform the responsible attending physician that the subject is in a clinical study and that relevant information may be obtained by contacting the investigator.

Subjects' parent(s)/LAR(s) must be instructed to keep subject cards in their possession at all times.

## **8.7. Holding rules and safety monitoring**

### **8.7.1. iSRC Review**

Periodic reviews of clinical safety data will be done by an internal Safety Review Committee (iSRC).

The iSRC members will include a GSK Biologicals' Global Clinical Research and Development Central Safety Physician, a Clinical Research and Development Lead, and a Senior Biostatistician as core members. These members will not be otherwise involved in the conduct of the study and will be independent from GSK's Pandemic Influenza Safety

Review Team. The iSRC members will have access to all available safety data. Other operational details will be described in an iSRC charter.

### 8.7.2. Holding Rules – primary series

**Table 20** lists criteria which will lead to suspension of any further administration of priming doses of vaccine (termed “holding rules”) to any participant until a review of available study safety data has occurred.

**Table 20 Holding Rules**

Holding Rule #	Event	# of subjects	Proportion of subjects
1a‡	If one subject experiences death or a life-threatening event	≥ 1	
1b‡	If one subject experiences any vaccine-related* SAE	≥ 1	
1c‡	If one subject is diagnosed with a potential immune-mediated disease	≥ 1	
1d†	If one subject is withdrawn from the study (by investigator request) following a Grade 3 vaccine-related AE*	≥ 1	
1e†	Any vaccine-related* local or general solicited AE leading to hospitalization, or vaccine-related* fever >40°C by any route, or necrosis at the injection site, within the 7-day post-vaccination period	≥ 1	
2a	Subjects reporting any Grade 3 solicited local AE in an investigational group, within the 7-day post-vaccination period		≥ 30%
2b	Subjects reporting any Grade 3 vaccine-related* solicited general AE in an investigational group, within the 7-day post-vaccination period		≥ 20%
2c	Subjects reporting any Grade 3 vaccine-related* unsolicited AE in an investigational group, within the 21-day post-vaccination period		≥ 20%

‡ Reported via eCRF within 24 hours

\* vaccine related implies that there is a reasonable possibility that the vaccine(s) contributed to the SAE/AE as determined by the Investigator.

[figure not shown]
† Investigators should refer to the local study contact information document to notify the study sponsor within 24 hours of any 1d or 1e events.

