**Epoch:**

An epoch is a self-contained set of consecutive timepoints or a single timepoint from a single protocol. Self-contained means that data collected for all subjects at all timepoints within that epoch allows to draw a complete

conclusion to define or precise the targeted label of the product (e.g. primary, booster, yearly immunogenicity follow-ups, and surveillance periods for efficacy or safety).

**eTrack:** GSK's tracking tool for clinical trials.

**Evaluable:** Meeting all eligibility criteria, complying with the procedures defined in the protocol, and, therefore, included in the according-to-protocol (ATP) analysis.

**Geometric mean titer:** The anti-log of the mean of the log (base 10) transformed inverse titers (the number X would denote the inverse of a titer expressed as "1:X"). Antibody titers below the cut-off of the assay are given an arbitrary value of half the cut-off for the purpose of GMT calculation.

**Immunological correlate of protection:** The defined immune response above which there is a high likelihood of protection in the absence of any host factors that might increase susceptibility to the infectious agent.

**Internal Safety Review Committee:** The internal safety review committee is a group of internal GSK experts not directly involved with the conduct of the study, who assess the progress of the study and the safety and efficacy data in an unblinded (on a subject level or treatment group level) fashion. Based on its review, the iSRC gives recommendations to the Clinical Project Team regarding study modification, continuation or termination.

**Investigational vaccine:** A pharmaceutical form of an active ingredient or placebo being tested or used as a reference in a clinical trial, including a product with a marketing authorisation when used in a way different from the approved form, or when used for an unapproved indication, or when used to gain further information about an approved use.

**(Synonym of  
Investigational Medicinal  
Product)** **Legally acceptable  
representative:** (The terms legal representative or legally authorized representative are used in some settings.) An individual or juridical or other body authorized under applicable law to consent, on behalf of a prospective subject, to the subject's participation in the clinical trial.

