### 8.7.3. Impact of sample size on holding rule assessment

The likelihood that a particular holding rule is met varies according to the total number of subjects expected to be evaluated at the time of an iSRC review. With 37 enrolled subjects and a cut off of 8/37, there is 90% chance that the holding rule 2b/2c is met for a vaccine with a true incidence rate of an event triggering a holding rule of 30%,

representing an unacceptable safety profile, and 95 % chance that the holding rule is not met for a vaccine with a true incidence of 10%. Refer to [Figure 2](#).

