### **9.2.2. Subject withdrawal from investigational vaccine**

A ‘withdrawal’ from the investigational vaccine refers to any subject who does not receive the complete treatment, i.e. when no further planned dose is administered from the date of withdrawal. A subject withdrawn from the investigational vaccine may not necessarily be withdrawn from the study as further study procedures or follow-up may be performed (safety or immunogenicity) if planned in the study protocol.

Information relative to premature discontinuation of the investigational vaccine will be documented on the Vaccine Administration page/screen of the eCRF. The investigator will document whether the decision to discontinue further vaccination/treatment was made by the subject’s parent(s)/LAR(s), or by the investigator, as well as which of the following possible reasons was responsible for withdrawal:

- Serious adverse event.
- Non-serious adverse event.
- Other (specify).

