8.2. SDD Stored analysis

Description	Analysis ID (SDD sub-folder)	Disclosure Purpose	Study Headline Summary (SHS) requiring expedited communication to Upper Management (Yes/No)	Reference for TFL
iSRC 1 to iSRC 11	E1_02 to E1_12	Internal	No	SAP/TFL associated to the Charter
iSRC 12 to iSRC 17	E1_13 to E1_18			
Day 42 Analysis	E1_13	CTR	Yes	TFL for Day 42 and Final Analysis
Final Analysis	E1_01	Study Report (SR) CTR	Yes	TFL for Day 42 and Final Analysis

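### Holding rule 1d covers only withdrawal from the study, so a child whose dose 2 is withheld for a non-serious Grade 3 related AE but who stays in follow-up triggers no single-case hold and no 24-hour notice

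*Protocol*

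**What the plan says.** Protocol section 8.7.2 introduces Table 20 as "criteria which will lead to suspension of any further administration of priming doses of vaccine", for any participant, until the available safety data have been reviewed. Rules 1a to 1e each act on a single child. Rules 2a to 2c act on a proportion of one group: at least 30% for Grade 3 solicited local AEs (2a), and at least 20% for Grade 3 related solicited general AEs (2b) and Grade 3 related unsolicited AEs (2c).

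Rule 1d is worded "If one subject is withdrawn from the study (by investigator request) following a Grade 3 vaccine-related AE". The footnote to Table 20 asks for sponsor notification within 24 hours of 1d and 1e events. The other 24-hour route, in Table 19, is for SAEs and potential immune-mediated diseases (pIMDs).

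Section 9.2 separates two statuses. Section 9.2.1 describes withdrawal from the study, after which no procedure, follow-up or data collection takes place. Section 9.2.2 describes withdrawal from the investigational vaccine, and states: "A subject withdrawn from the investigational vaccine may not necessarily be withdrawn from the study". Under 9.2.2 the decision may be the parents' or the investigator's, and a non-serious adverse event is one of the listed reasons. The data are captured: "Information relative to premature discontinuation of the investigational vaccine will be documented on the Vaccine Administration page/screen of the eCRF".

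On oversight by the internal Safety Review Committee (iSRC), section 8.7.1 says: "The iSRC members will have access to all available safety data". The Glossary adds that "the iSRC gives recommendations to the Clinical Project Team regarding study modification, continuation or termination". SAP section 8.2 lists iSRC analyses 1 to 11 and "iSRC 12 to iSRC 17".

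**The concern.** The sponsor has already decided that one child removed by an investigator after a Grade 3 related AE is enough to stop priming and review the data. As worded, that decision depends on which of two statuses the site records. If the site takes the child out of the study, priming stops for everyone. If it withholds dose 2 and keeps the child under observation, which gives better safety data, nothing is triggered by that single case.

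The situation is plausible. Section 1.2 says the trial was prompted by more fever after a second or third dose in some earlier studies in young children, so an investigator who sees a Grade 3 fever after dose 1 has a reason to be cautious about dose 2. The affected child is already protected, because the dose is withheld. What is at stake is how soon the sponsor and the iSRC learn of the investigator's decision while other children are still receiving priming doses.

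**Working it through.** **Step 1. The plan's own figure.** Section 8.7.3 uses a cut-off of 8 of 37 for rules 2b and 2c. It states a 90% chance that the rule is met at a true incidence of 30%, and a 95% chance that it is not met at 10%. Exact binomial:

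- P(X ≥ 8 | n = 37, p = 0.30) = 0.905, which agrees with 90%.
- P(X ≤ 7 | n = 37, p = 0.10) = 0.973, somewhat above the stated 95%.

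Neither figure concerns rule 1d, for which the protocol gives no operating characteristic.

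**Step 2. Test the single-case rules.** Take a child with related fever of 39.0 to 40°C after dose 1 (score 3 in the temperature scale under Table 18). The event is not serious, the investigator withholds dose 2, and the child stays in follow-up.

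| Rule | Trigger | Met? |
|---|---|---|
| 1a | Death or life-threatening event | No |
| 1b | Vaccine-related SAE | No; section 8.2.3.2.2 separates Grade 3 from serious |
| 1c | pIMD diagnosis | No |
| 1d | Withdrawn from the study by investigator request | No; the status is the one in 9.2.2 |
| 1e | Related solicited AE with hospitalisation, related fever above 40°C, or injection-site necrosis | No |

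The 24-hour routes are SAEs and pIMDs (Table 19) and 1d and 1e events (Table 20 footnote). None applies.

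**Step 3. Test the group rules in a full group of 37.** The required count is the smallest k for which k/37 reaches the threshold.

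- 20% (2b, 2c): 7/37 = 18.9% and 8/37 = 21.6%, so k = 8.
- 30% (2a): 11/37 = 29.7% and 12/37 = 32.4%, so k = 12.

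One child therefore cannot meet a group rule in a full group. If the denominator is the children evaluated so far (an assumption), one child reaches 20% when five or fewer have been evaluated (1/5 = 20%).

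**Step 4. What still captures the event.** The AE counts toward 2a or 2b if it falls in the 7-day window, or toward 2c in the 21-day window. It is also in the data the iSRC sees. SAP 8.2 lists 11 + 6 = 17 iSRC analyses, without dates.

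**Step 5. How much time a 24-hour notice would gain.** The notes to Table 17 say that solicited diary data from dose 1 are reviewed at the Day 21 visit. The solicited window ends on Day 6, so a diary-reported event may be 21 − 6 = 15 days old or more when the site first sees it, unless the parents call. The 24-hour clock would then start at about the time dose 2 is due.

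**The case against.** The strongest reply is that this is a wording matter with little practical effect. The no-further-follow-up definition in 9.2.1 is framed for analysis, and the same section tells investigators to follow children withdrawn for an AE until it resolves. Section 6.5 refers to withdrawal under Section 9 without saying which kind. The authors may have meant 1d to include vaccine-only stops. The iSRC charter and the local study contact document, where operating detail would sit, are not among the documents. This stands as a reason for moderate confidence, but it does not supply the missing words. Section 9.2.2 states the distinction plainly, and no Table 20 rule refers to stopping vaccine.

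A second reply is that the plan deliberately handles related fever of 39.0 to 40°C by proportion, through 2b, and keeps single-case holds for graver events. That is fair for the fever alone. But 1d already acts on one child with a Grade 3 AE of any kind when the investigator removes that child from the study. The point concerns that decision, not the temperature threshold.

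A third reply concerns speed. Diary review waits for Day 21, and the site records degrees while the sponsor assigns the temperature score, so little time is gained. If the 17 iSRC analyses were evenly spread (an assumption), they would fall about every 112/17 = 7 days over a 112-day priming period (91 days of enrolment plus 21), or about every 506/17 = 30 days over the whole study (91 + 415 days). This reply largely stands, and the gain should be called modest.

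A reader might infer that the safety signal is lost. The documents do not support that: the event is recorded, counted and visible, and the iSRC can recommend stopping whether or not a Table 20 rule is met. A reader might also infer that up to 7 or 11 such children could pass unnoticed in a group. That would require every child with a qualifying Grade 3 event to have dose 2 withheld. Nor does the 10% incidence in 8.7.3 give a count. It implies 37 × 0.10 = 3.7 children with such an event per group, the missed children are a subset of those, and the documents do not say what fraction.

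**Conclusion.** The gap is real but narrow. By the protocol's own definitions, withholding the second priming dose for a non-serious Grade 3 vaccine-related AE while the child stays in the study triggers neither a single-case hold nor a 24-hour notice. What is lost is that one-child response; the remaining safeguards are periodic iSRC review and group rules that need 8 or 12 of 37 children in a full group.

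The documents give no frequency for the case, and none can be derived from them. The conclusion rests on reading rule 1d literally together with 9.2.1 and 9.2.2, and on the iSRC charter adding no criterion of its own. No efficacy or safety analysis changes. The change is worth making because it is cheap and makes the rule consistent with a threshold the sponsor has already chosen; the trial's safety oversight does not fail without it.

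**What to change.** Reword rule 1d along these lines: *withdrawn from the study, or from the remaining priming dose, by investigator decision following a Grade 3 vaccine-related AE*. The existing 24-hour footnote then applies, and a booster withheld at Day 385 stays outside the rule. Add a prompt ad hoc iSRC review so that any hold is short. If the sponsor considers an automatic hold excessive for a vaccine-only stop, it should at least extend the 24-hour notice and the ad hoc review to such stops. If the exclusion is deliberate, the protocol should say so.

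The edit is one phrase and needs no new data, since 9.2.2 already records the reason and who decided. The downside is occasional extra notices and temporary holds of priming for all participants. A long hold can move dose 2 outside the 18 to 25 day interval in Table 7, which removes children from the according-to-protocol immunogenicity cohort.

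To gauge that cost, assume even enrolment of 185 children over about 91 days (185/91 = 2.03 per day) and a hold of H days. The number pushed out lies between (H − 7) × 2.03, for children whose whole 8-day window falls inside the hold, and (H − 4) × 2.03, for children booked for exactly Day 21; negative values count as zero.

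- H = 4: none.
- H = 7: 0 to 6.
- H = 14: 14 to 20.

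The planned margin is 37 − 34 = 3 per group, or 15 in all. The cost is therefore small only if the review is prompt. Any other Table 20 hold of the same length carries the same cost.
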